### 1. Introduction

Pancreatic ductal adenocarcinoma (PDAC) is associated with a very poor prognosis, in part due to the development of disease recurrence in up to 80% of patients within two years after radical resection. Despite the high incidence of recurrent pancreatic cancer, current national guidelines do not contain specific recommendations for surveillance after resection of pancreatic ductal adenocarcinoma. The lack of Dutch or European guidelines regarding follow-up has led to different surveillance strategies among pancreatic surgeons in the Netherlands. A recent nationwide survey carried out under Dutch pancreatic surgeons showed that generally a symptomatic surveillance strategy is favored, consisting of regular outpatient visits without routine tumor marker testing or imaging. The impact of this current practice on the detection and treatment of recurrent pancreatic cancer and overall survival has not been well established.

## 2. Aim

The aim of this study is to evaluate current surveillance strategies after primary resection of pancreatic cancer in the Netherlands, with regard to the detection and treatment of recurrent disease.

## 3. Intervention

Not applicable.

## 4. Sample size

All patients undergoing resection for primary pancreatic ductal adenocarcinoma between 2011 and 2016.

## 5. Study design

A retrospective observational cohort study in all DPCG-affiliated centers.

## 6. Primary outcome measures

- Incidence of PDAC recurrence
- Patterns of PDAC recurrence (asymptomatic vs. symptomatic; first site of recurrence; early vs. late recurrence)
- Treatment of PDAC recurrence

## 7. Secondary outcome measures

- Symptoms at time of (suspected) recurrence
- Performance score at time of recurrence detection
- Use of imaging procedures during follow-up
- Number of histologically confirmed recurrences
- Recurrence-free survival
- Post-recurrence survival
- Overall survival

## 8. Inclusion criteria

- Patients with PDAC confirmed by pathological examination
- Patients undergoing a pancreatic resection (PPPD, Whipple, distal pancreatectomy or total pancreatectomy)

## 9. Exclusion criteria

- Patients with 30-day postoperative mortality

## 10. Participating centers

All DPCG-affiliated hospitals.

## 11. Data collection

The following data will be collected: age, sex, BMI, ASA score, preoperative CA 19-9 level, operation procedure, resection margin status (R0/R1/R2), tumor differentiation, tumor size, TNM stage, total lymph nodes, positive lymph nodes, microscopic perineural invasion, microscopic perilymphatic invasion, adjuvant therapy, date start adjuvant treatment, time between surgery and start date adjuvant treatment, number of cycles adjuvant treatment received, use and type of imaging procedures, presence of recurrence, presence of histological evidence for recurrence and pathologic results, recurrence site, date of recurrence, symptomatic recurrence, asymptomatic recurrence, type of treatment after recurrence, date of operation, date of death, date of last follow-up.

Asymptomatic recurrence is defined as recurrent pancreatic cancer detected as an incidental finding following additional examination for other reasons or by imaging requested by the patient. If recurrent pancreatic cancer is discovered due to a significant patient-initiated complaint that is new or has been increased in severity or frequency, disease recurrence will be defined as symptomatic.

Patterns of recurrence are furthermore categorized using four categories: 1) isolated local recurrence: recurrence in the pancreatic remnant or in the surgical bed, such as soft tissue along the celiac or superior mesenteric artery, aorta or around the pancreatojejunostomy site; 2) isolated distant recurrence: recurrence restricted to a single organ or site; 3) local + distant recurrence: simultaneous occurrence of both isolated local recurrence and isolated distant recurrence; 4) multiple recurrence: recurrence at multiple distant sites and/or carcinomatosis.

Early disease recurrence is defined as recurrence < 10 months after surgery, late disease recurrence is defined as recurrence ≥ 10 months after surgery. This cutoff point was found to be the most significant value for showing differences in post-recurrence survival.

Overall survival (OS) and post-recurrence survival are defined as the time from the date of operation (OS) or the date of recurrence (post-recurrence survival) to either death from any cause or last follow-up. Recurrence-free survival (RFS) is defined as the time interval between the date of the operation and either date of recurrence or last follow-up if recurrence is not observed.

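### Preoperative treatment is neither an exclusion nor a collected item, so any pretreated patients cannot be told apart from upfront resections

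*Combined protocol and SAP*

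**What the plan says.** Section 4 defines the cohort as "All patients undergoing resection for primary pancreatic ductal adenocarcinoma between 2011 and 2016". Section 8 asks for two things: "Patients with PDAC confirmed by pathological examination", and one of four named types of pancreatic resection. Section 9 has one exclusion, "Patients with 30-day postoperative mortality". None of the three mentions treatment before surgery.

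The perioperative treatment items in section 11 are "adjuvant therapy, date start adjuvant treatment, time between surgery and start date adjuvant treatment, number of cycles adjuvant treatment received". The only item labelled preoperative is a laboratory value, "preoperative CA 19-9 level".

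The aim in section 2 is to "evaluate current surveillance strategies after primary resection of pancreatic cancer in the Netherlands". The adjective primary there could mean upfront surgery, but no eligibility criterion says so.

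Section 11 measures overall survival (OS) and the 10-month early/late split from surgery, and defines recurrence-free survival (RFS) as "the time interval between the date of the operation and either date of recurrence or last follow-up". Post-recurrence survival runs from the date of recurrence. Section 12 plans univariable and multivariable Cox models for post-recurrence survival and does not name the covariates.

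**The concern.** A patient given chemotherapy or chemoradiotherapy before resection meets every criterion and carries no flag. Three things follow for any such patient.

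- **Baseline values.** CA 19-9, tumour size, stage, nodal counts and margin status may reflect the disease after treatment. They are pooled with values from untreated tumours.
- **Time origin.** For an upfront patient, the operation is the start of treatment. For a pretreated patient it comes later, and only patients who still reached resection are counted. The same number of months from surgery does not mean the same point in the disease course.
- **Adjuvant category.** A pretreated patient with no postoperative therapy falls in the same category as a patient who had no perioperative treatment.

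Early versus late recurrence is part of a primary outcome, and so is treatment of recurrence, which earlier therapy could influence. If preoperative treatment is related both to these features and to survival after recurrence, it confounds the early/late comparison and the Cox models. Analysts cannot describe or adjust for an item that was never extracted.

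**Working it through.** The plan states no sample size, event count or treatment share, so there is no figure of its own to reproduce. The check is a reading of the text followed by an illustration on assumed inputs.

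**Step 1: can a pretreated patient enter, and be found?**

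| Place | Content | Bars or identifies a pretreated patient? |
|---|---|---|
| Section 2 | Aim refers to primary resection | Ambiguous; not a criterion |
| Section 4 | All resections for primary PDAC; primary describes the tumour | No |
| Section 8 | Pathological confirmation and a listed resection | No |
| Section 9 | Death within 30 days | No |
| Section 11 | Four adjuvant items; no preoperative treatment item | No |

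Section 11 also lists no date of diagnosis and no date of first treatment. A long interval before surgery therefore cannot serve as an indirect marker.

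**Step 2: the early/late clock.** Suppose preoperative treatment starts *m* months before surgery. A recurrence *t* months after surgery is then *t* + *m* months after the start of treatment. The rule *t* < 10 becomes *t* + *m* < 10 + *m*, so the cutoff lies at 10 + *m* months for that patient and at 10 months for an upfront patient. Selection of patients who still reached resection acts as well, and the documents do not allow the net direction to be determined.

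**Step 3: make-up of the group without adjuvant therapy.** All inputs are assumptions: *p* is the share of the cohort that is pretreated, *g* the share of pretreated patients without adjuvant therapy, and *h* the same share in upfront patients.

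Share of that group that is pretreated = *pg* / [*pg* + (1 − *p*)*h*]

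The range column uses *g* from 30% to 70% and *h* from 30% to 50%. Its low end pairs *g* = 30% with *h* = 50%, and its high end pairs *g* = 70% with *h* = 30%.

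| *p* | *g* = 50%, *h* = 35% | Range |
|---|---|---|
| 0% | 0% | 0% |
| 2% | 0.010 / (0.010 + 0.343) = 2.8% | 0.006/0.496 = 1.2% to 0.014/0.308 = 4.5% |
| 5% | 0.025 / (0.025 + 0.3325) = 7.0% | 0.015/0.490 = 3.1% to 0.035/0.320 = 10.9% |
| 10% | 0.050 / (0.050 + 0.315) = 13.7% | 0.030/0.480 = 6.3% to 0.070/0.340 = 20.6% |
| 15% | 0.075 / (0.075 + 0.2975) = 20.1% | 0.045/0.470 = 9.6% to 0.105/0.360 = 29.2% |

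When *g* = *h* the share equals *p*. Pretreated patients are over-represented in this group only if they receive adjuvant therapy less often than upfront patients.

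**Step 4: pooled recurrence at 10 months.** If the two groups differ by *d* points, the pooled figure differs from the upfront-only figure by *p* × *d*. With *d* assumed to be 10 points, that is 0.5 points at *p* = 5% and 1 point at *p* = 10%.

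**The case against.** The strongest reply is that the plan describes all resected patients, as section 4 says. Incidence, patterns and treatment of recurrence are valid descriptions of that population whatever came before surgery, and the operation is the natural time origin for a study of follow-up after resection. That stands: the population is defined, and the overall descriptive results are not invalid. What is missing is the ability to describe the mix and adjust for it.

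A reader might go further than the documents allow in five ways.

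- **That pretreated patients are in the cohort.** The documents mention none and give no share. The aim may have meant upfront surgery only. The point is conditional.
- **That such patients are miscoded as systemically untreated.** The field is adjuvant therapy, so recording none would be literally correct. The error arises only if that group is later read as having had no perioperative treatment.
- **That stage, nodes or margin are mismeasured.** They are recorded as observed. What changes is their meaning, which is heterogeneity and not measurement error.
- **That the hazard ratios are biased.** Section 12 names no covariates, and the Cox clock starts at recurrence, so the operation-based origin does not enter that model as its time scale. Confounding is possible; its direction and size are not established.
- **That the gap can never be repaired.** Section 16 keeps a code list linking data to subjects, so charts could be reopened. Doing so in every centre would be more work than collecting the item at the first extraction.

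The wording of the aim does not close the gap. Without a criterion, centres may read it differently, and without an item the coordinating team cannot check.

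**Conclusion.** The point holds in conditional form. The plan neither excludes nor records preoperative treatment, so any pretreated patients are eligible and cannot be distinguished from upfront resections. This can confound the early/late comparison and the post-recurrence Cox models.

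The consequence runs from nil to material. On the central assumed rates, the mixing in the group without adjuvant therapy is about 7% at a 5% pretreated share and 14% at a 10% share. The effect on pooled 10-month recurrence is small by comparison. Every input is an assumption. What does not depend on them is that the planned dataset could not show the share to be negligible.

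A reader might infer that the main results should be limited to upfront resections. The documents do not support that as a requirement, because it would replace the stated population of all resected patients with a subset.

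**What to change.** Add one item to section 11: preoperative treatment (yes/no, type, start and stop date). In section 12:

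- keep all resected patients as the main population;
- report recurrence and the early/late results by preoperative treatment;
- include it as a candidate covariate in the Cox models for post-recurrence survival;
- add a sensitivity analysis restricted to upfront resections.

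Alternatively, if the aim was meant to cover upfront surgery only, state that in sections 8 and 9 and use the new item at screening to enforce it.

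The cost is a small amount of extra chart extraction in each centre and one more candidate term in the models. The work is least if the item is added before extraction is complete.

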## 12. Statistical analyses

Descriptive statistics will be obtained. Continuous variables are expressed as median and range, unless specified otherwise, and categorical values as number (percentage). The proportion of patients receiving imaging procedures for each month of follow-up will be calculated by dividing the amount of patients receiving one or more imaging procedure(s) for the detection of recurrence by the amount of uncensored patients. Censoring occurs at date of recurrence, death, or last follow-up if recurrence does not occur. Kaplan-Meier curves are used to

estimate median OS, RFS and post-recurrence survival with corresponding 95% confidence intervals. Univariable and multivariable analyses will be performed using Cox proportional hazard models to identify potential predictive factors for post-recurrence survival. A two-tailed P value of <0.05 is considered to indicate statistical significance. Statistical analysis will be performed with SPSS statistical software, version 23.0 (SPSS Inc., Chicago, IL).

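### The first primary outcome, recurrence incidence, has no time horizon, follow-up cut-off or stated estimator; secondarily, RFS as defined leaves out death and is a time to recurrence

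*Combined protocol and SAP*

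**What the plan says.** **Incidence.** Section 6 names "Incidence of PDAC recurrence" first among the primary outcomes and adds nothing on when or how it is measured. Section 11 lists the underlying variable among the data items: "use and type of imaging procedures, presence of recurrence". Section 12 reports "categorical values as number (percentage" and reserves Kaplan-Meier curves to "estimate median OS, RFS and post-recurrence survival with corresponding 95% confidence intervals". Incidence is not in that list.

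**Follow-up.** Section 4 takes in "All patients undergoing resection for primary pancreatic ductal adenocarcinoma between 2011 and 2016". No data cut-off or minimum follow-up appears anywhere, and Section 15 treats study duration as not applicable because the study is retrospective. Section 9 removes only patients who died within 30 days of surgery, so later deaths without recurrence stay in the cohort.

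**RFS.** Section 11 defines it as "the time interval between the date of the operation and either date of recurrence or last follow-up if recurrence is not observed". The sentence just before it, for overall and post-recurrence survival, runs "to either death from any cause or last follow-up". The plan's one censoring sentence is in Section 12, directly after the monthly imaging proportion: "Censoring occurs at date of recurrence, death, or last follow-up if recurrence does not occur".

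**The concern.** A proportion with recurrence has a meaning only at a stated time since surgery. A patient operated on early in 2011 can have about six years more follow-up than one operated on late in 2016. A plain percentage averages over these unequal periods. It rises as the cut-off is moved later, and it also depends on losses to follow-up. Two analysts who both follow the plan could report different values for its first primary outcome from the same patients.

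The RFS definition is a smaller matter. The label suggests that death ends the recurrence-free state, but the definition counts recurrence only. A reader who takes the label at face value would misread the Kaplan-Meier median.

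**Working it through.** The plan states no event rate, sample size calculation or follow-up figure, so there is nothing of its own to reproduce. The definitional points follow from the text above; the arithmetic only shows how large they could be.

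**Inputs**
- Entry window: 2011 to 2016, 72 months (Section 4).
- Assumed: 24-month documented recurrence c = 60%, 70% or 80%. The only recurrence figure in the documents is the background figure in Section 1, up to 80% within two years.
- Assumed: 24-month death without documented recurrence d = 2%, 5%, 10% or 15%.
- Assumed: constant hazards, uniform accrual, no loss to follow-up, and a cut-off x = 12, 24 or 36 months after the end of 2016.

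**Formulas**
- Total hazard t = -ln(1 - c - d)/24; recurrence hazard r = t × c/(c + d).
- Cumulative incidence at u months: (r/t)(1 - exp(-tu)).
- Crude percentage: its mean over u from x to 72 + x, which is (r/t)[1 - (exp(-tx) - exp(-t(72 + x)))/(72t)].
- Median with deaths censored: ln2/r. Median with deaths counted: ln2/t.
- One minus Kaplan-Meier at 24 months with deaths censored: 1 - exp(-24r).

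**Worked cell, c = 70%, d = 10%**
- t = -ln(0.20)/24 = 0.06706 per month; r = 0.06706 × 0.70/0.80 = 0.05868 per month.
- Crude percentage at x = 12: 0.875 × [1 - (0.4472 - 0.0036)/4.828] = 79.5%. At x = 24 and 36: 83.9% and 85.9%. The 24-month value is 70% throughout.
- If both hazards halve after 24 months: 76.7%, 80.9% and 83.1%.
- One minus Kaplan-Meier at 24 months: 1 - exp(-24 × 0.05868) = 75.5%, against a cumulative incidence of 70%.
- Median: ln2/0.05868 = 11.8 months with deaths censored; ln2/0.06706 = 10.3 months with deaths counted.

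**Whole grid**

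| c | Crude percentage, 36- minus 12-month cut-off, for d = 2 / 5 / 10 / 15% (points) | Median, censored minus counted, for d = 2 / 5 / 10 / 15% (months) |
|---|---|---|
| 60% | 12.0 / 10.8 / 8.9 / 7.1 | 0.6 / 1.3 / 2.3 / 3.0 |
| 70% | 9.5 / 8.3 / 6.4 / 4.8 | 0.4 / 0.9 / 1.5 / 1.9 |
| 80% | 6.6 / 5.4 / 3.7 / 2.0 | 0.2 / 0.6 / 0.9 / 1.0 |

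With halved hazards after 24 months, the shift in the crude figure runs from 2.1 to 10.4 points. With no deaths without recurrence, the two medians coincide.

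**Direction of the median effect.** Counting deaths can only lower the curve, so the median with deaths censored is never shorter. It need not be longer. Take five patients: one death at time 1 and recurrences at 2, 3, 4 and 5. With the death censored the curve is 0.75 at time 2 and 0.50 at time 3. With it counted the curve is 0.80, 0.60 and 0.40 at times 1, 2 and 3. The median is 3 both ways.

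**The case against.** **The plan never says it will report a crude percentage.** True: that is an inference from the only summary in Section 12 that fits a yes/no variable. What the text establishes is that horizon, cut-off and estimator are not stated.

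**The RFS curve already shows recurrence over time.** This stands in part. As defined, RFS is a time to recurrence, and Kaplan-Meier allows for unequal follow-up. But only the median is planned, and reading incidence off a curve with deaths censored overstates it (75.5% against 70% in the worked cell).

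**The study is descriptive.** No test or model uses incidence or RFS; the Cox models concern post-recurrence survival. This limits the harm, and makes the RFS part alone a minor clarification. It does not excuse leaving the first primary outcome undefined.

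**The larger figures rest on assumptions.** They do. The 12.0-point shift is the 60%/2% cell and the 3.0-month difference the 60%/15% cell. At 80% recurrence the ranges are 2.0 to 6.6 points and 0.2 to 1.0 months. Since the background figure is an upper bound, lower recurrence is not excluded.

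A reader might also infer more than the documents support:
- That the study will be compared with the two-year 80% figure. That figure is introductory background, and no comparison is planned.
- That the censoring sentence in Section 12 settles how RFS treats death. It is written for the imaging denominator and also lists recurrence as a censoring time, so it cannot carry over to RFS unchanged.
- That a 2018 item in the reference list rules out earlier cut-offs. A citation does not date the data cut-off. Earlier cut-offs remain possible and would widen the range shown.

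**Conclusion.** The point holds and should be fixed before analysis. Its weight rests on the first primary outcome, whose value depends on a cut-off the plan does not state. Under the assumed rates, constant hazards and no loss, moving that cut-off from 12 to 36 months after 2016 changes a crude percentage by 2.0 to 12.0 points. The true size is unknown because the documents give neither the rate of death without recurrence nor the length of follow-up.

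The RFS omission is real but secondary. The outcome is mislabelled as written, and its median is the same as or longer than one that counts death, by 0.2 to 3.0 months over the assumed grid. The stronger statement, that the median is always longer when someone dies without recurrence before it, is not correct, as the five-patient example shows.

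**What to change.** 1. **Primary outcome.** Report the cumulative incidence of documented recurrence at fixed times, such as 12 and 24 months after operation, with 95% confidence intervals. Treat death without documented recurrence as the competing event (Aalen-Johansen estimator). State the follow-up cut-off date.
2. **RFS.** Define it as time from operation to recurrence or all-cause death, whichever comes first, censored at last follow-up in patients alive and free of recurrence. Alternatively, rename it time to recurrence and say that deaths are censored at the date of death. State that the censoring sentence in Section 12 applies to the imaging proportion only.
3. **Deaths without documented recurrence.** Report their number. Section 1 describes follow-up driven by symptoms without routine imaging, so some may be undetected recurrences. As a sensitivity bound, count them all as recurrences: in the worked cell, 70% + 10% = 80% at 24 months.

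The cost is protocol wording; Section 11 already collects the dates of operation, recurrence, death and last follow-up. Two downsides: median RFS may become shorter once death counts, and the cumulative incidence analysis may need software other than the named SPSS 23.

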## 12. Statistical analyses

Descriptive statistics will be obtained. Continuous variables are expressed as median and range, unless specified otherwise, and categorical values as number (percentage). The proportion of patients receiving imaging procedures for each month of follow-up will be calculated by dividing the amount of patients receiving one or more imaging procedure(s) for the detection of recurrence by the amount of uncensored patients. Censoring occurs at date of recurrence, death, or last follow-up if recurrence does not occur. Kaplan-Meier curves are used to

estimate median OS, RFS and post-recurrence survival with corresponding 95% confidence intervals. Univariable and multivariable analyses will be performed using Cox proportional hazard models to identify potential predictive factors for post-recurrence survival. A two-tailed P value of <0.05 is considered to indicate statistical significance. Statistical analysis will be performed with SPSS statistical software, version 23.0 (SPSS Inc., Chicago, IL).

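### Recurrence treatment is listed without a start date, so if it enters the post-recurrence Cox model it can only be a fixed covariate, with a hazard ratio biased towards benefit

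*Combined protocol and SAP*

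**What the plan says.** Section 11 defines post-recurrence survival as running from "the date of recurrence (post-recurrence survival) to either death from any cause or last follow-up". Its data list ends with "type of treatment after recurrence, date of operation, date of death, date of last follow-up", so recurrence treatment is recorded by type and no start date is listed. For adjuvant therapy the same list does give timing: "date start adjuvant treatment, time between surgery and start date adjuvant treatment".

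Section 12 plans univariable and multivariable "Cox proportional hazard models to identify potential predictive factors for post-recurrence survival", tested at the two-sided 5% level. It names no candidate covariates and does not say how a factor that arises after the date of recurrence would be handled.

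Treatment of recurrent disease is part of the aim (section 2) and one of the three primary outcome measures (section 6). Section 12 also provides for categorical variables to be summarised as counts and percentages, which would cover treatment as a purely descriptive outcome.

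**The concern.** Treatment for recurrence normally starts some time after recurrence is found. A patient must live through that interval to be recorded as treated. If treatment is coded as a fixed yes/no from the date of recurrence, two things follow. Patients who were meant to be treated but died first are counted as untreated, and the waiting time of those who did start is counted as treated time although no death could occur in it. Both push the hazard ratio below 1 when treatment does nothing (immortal time bias).

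Without a start date the usual remedies cannot be built: neither a time-dependent covariate nor treatment status at a landmark can be constructed. At stake is a result that would attract attention, namely an apparent survival benefit of treating recurrence that arises from the coding alone.

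**Working it through.** **What the documents supply.** Time origin (date of recurrence), event (death from any cause), model (Cox) and the two-sided 5% level. They give no number of recurrences, post-recurrence survival, start delay or treated share. There is therefore no figure in the plan to reproduce, and every numerical input below is an assumption.

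**Hand calculation for one case.** Assume 400 recurrences, exponential survival with median 6 months, no treatment effect, no censoring, 40% intended for treatment, and a start exactly 1 month after recurrence.

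- Hazard: λ = ln 2 / 6 = 0.1155 per month; mean survival 1/λ = 8.656 months.
- Probability of living to the start: exp(−0.1155 × 1) = 0.891.
- Intended: 0.40 × 400 = 160. Start treatment: 160 × 0.891 = 142.5. Die first: 17.5.
- Coded treated: 142.5 deaths over 142.5 × (1 + 8.656) = 1,376 patient-months, a rate of 0.1036.
- Coded untreated: 240 + 17.5 = 257.5 deaths over 240 × 8.656 + (160 × 8.656 − 1,376.4) = 2,086 patient-months, a rate of 0.1234.
- Rate ratio: 0.1036 / 0.1234 = 0.84, although the true ratio is 1.00.

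Now move the 142.5 waiting months to the untreated side, which is what a start date permits. Treated: 142.5 / (1,376.4 − 142.5) = 0.1155. Untreated: 257.5 / (2,086.0 + 142.5) = 0.1155. The ratio is 1.00.

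**Simulation over a range.** Null effect; exponential survival with medians 4, 6 and 10 months; start delay uniform on 0.5 to 1.5 times a mean of 0.5, 1, 1.5 or 2 months; 20%, 40% or 60% intended; univariable Cox model, Wald p<0.05; no censoring unless stated.

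| Assumed case | Intended 60% | 40% | 20% |
|---|---|---|---|
| Median 6, delay 1: fixed-covariate HR | 0.78 | 0.84 | 0.88 |
| Same, false p<0.05, 400 recurrences | 71% | 38% | 15% |
| Same, 200 recurrences | 44% | 21% | 9% |
| Same, 400 recurrences, 20% random censoring | 78% | 44% | 17% |
| Mild end (median 10, delay 0.5), 400 recurrences | 13% | 8% | 5% |
| Range over all cases, 400 recurrences | 13%–100% | 8%–99% | 5%–72% |

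Over all cases the fixed-covariate HR is 0.56 to 0.95 with 40% to 60% intended, and 0.70 to 0.96 with 20%.

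A second simulation with other assumptions (800 recurrences; medians 4, 6 and 9 months; constant or exponential delays; 30% or 60% intended; censoring uniform from 6 to 36 months) gave HRs of 0.52 to 0.93 and false significance in 11% to 100% of runs.

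**With the start date available.** In the first simulation, time-dependent coding and an 8-week landmark each gave HRs of 0.99 to 1.02 and about 4% to 6% rejections. The landmark removes patients who die before 8 weeks (56 / 30.44 = 1.84 months): 1 − exp(−ln 2 × 1.84 / 10) = 12% at median 10 months, and 1 − exp(−ln 2 × 1.84 / 4) = 27% at median 4 months.

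**The case against.** The strongest objection is that the faulty analysis appears nowhere in the documents. Section 12 names no covariates, does not propose Kaplan-Meier curves split by treatment, and can serve treatment as an outcome with counts and percentages. The only factor the plan ties explicitly to post-recurrence survival is early versus late recurrence, of which section 11 says "This cutoff point was found to be the most significant value for showing differences in post-recurrence survival". This stands. A reader might infer that the plan contains an immortal time error; the documents do not support that.

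Second, the data list is not complete. "Performance score at time of recurrence detection" is a secondary outcome but is not listed, and "use and type of imaging procedures" carries no dates although section 12 needs imaging by month of follow-up. A reader might infer that the start date will not be collected; its absence from this list does not show that. Nor do the documents support a claim that adding it later would mean returning to every center's records: they do not say what has been abstracted or when.

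Third, the size rests wholly on assumed inputs, and the false-positive range is too wide to say how much would be at stake in this study. The simulations are univariable, whereas the plan also has multivariable models. This stands too. The figures show that the bias can matter, not that it will.

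Fourth, correct coding leaves confounding by fitness for treatment in place. That is true, but it is a separate bias and no reason to accept one that a single date removes.

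**Conclusion.** The point holds as a conditional risk and is best labelled a cheap improvement. Treatment of recurrence is a likely candidate in an open search for predictors of post-recurrence survival, and the listed data would permit only the biased coding. The direction is certain whenever treatment starts after the date of recurrence and is coded as fixed. The size is not known. It grows with longer delay, shorter survival and a larger treated share, and is close to nothing with a short delay, long survival and few treated. It does not touch the descriptive reporting of treatment or the Kaplan-Meier medians for the cohort as a whole.

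**What to change.** Add the date on which treatment for recurrence started to the data list in section 11. In section 12, name the candidate Cox covariates in advance and say whether treatment is among them. If treatment is modelled, or used to split survival curves from the date of recurrence, either enter it as a time-dependent covariate or use one prespecified landmark (for example 8 weeks after recurrence), with treatment status classified at the landmark among patients still alive and in follow-up. If the date cannot be obtained, keep treatment out of the Cox models and report it descriptively.

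The cost is one extra chart date per treated recurrence and a slightly more complex model. A landmark drops the earliest deaths. Descriptive reporting needs no new data but gives no estimate for treatment. Because fitness for treatment still confounds the comparison under either coding, the plan should also say that the hazard ratio is not to be read as a treatment effect.
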